	
During the study period, all subjects will be evaluated for response by CT and/or MRI. Evaluations are to be obtained at approximately cycles 3, 6, and 12. Following cycle 12, evaluations should occur at least every 12 cycles unless clinically indicated sooner. Subjects followed for PFS off treatment should have scans completed per institutions standard of care and reported in the EDC until progressive disease or subject begins another anti-cancer treatment. Date of progression, beginning of new treatment, and/or death should be entered in the eCRF. Subjects should remain on study treatment until the occurrence of definitive disease progression, unacceptable toxicity, or withdrawal from the study due to investigator discretion or other reasons. Subjects who discontinue from study treatment and have not progressed should continue to be followed for progression.
																								

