### 4.1 OVERVIEW OF STUDY DESIGN

---

This Companion Study is intended for subjects who previously enrolled to the parent trial [UTX-TGR-304](#). Subjects from Treatment Arms B, C, and D with disease progression confirmed by the independent review committee (IRC), may be enrolled into this Companion Study. At the end of the UTX-TGR-304 study, non-progressed subjects from Treatment Arm A may also be enrolled to this Companion Study. Subjects from Treatment Arms B, C, and D may start treatment with ublituximab + TGR-1202, while subjects entering the Companion Study from Treatment Arm A may continue their treatment as specified by this protocol. All subjects enrolled to the Companion Study should receive ublituximab in combination with TGR-1202 (at the same dose and schedule as the Treatment Arm A in UTX-TGR-304) until they show disease progression, are unable to continue treatment for any reason such as lack of tolerability, or until the treatment is commercially available.

During the study period, all subjects will be evaluated for response by CT and/or MRI. Evaluations are to be obtained at approximately cycles 3, 6 and 12. Following cycle 12, evaluations should occur at least every 12 cycles unless clinically indicated more frequently. Subjects should remain on study treatment until the occurrence of definitive disease progression, unacceptable toxicity, or withdrawal from the study due to investigator decision or other reasons. Subjects who discontinue from study treatment (either for toxicity or physician choice) and have not progressed should continue to be followed for progression per institutional standard of care and reported in eCRF. Date of progression, beginning of new treatment, and/or death should be entered in the eCRF.

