### 4.4 DISCONTINUATION FROM STUDY TREATMENT

---

Subjects will be discontinued from study treatment for any of the following reasons:

- Disease progression
- Intolerable toxicity related to study drug
- Subject requests to withdraw consent or discontinue treatment
- Pregnancy
- Inability of the subject to comply with study requirements
- Conditions requiring therapeutic intervention not permitted by the protocol
- Non-compliance/lost to follow-up
- Investigator discretion
- Discontinuation of the study by the Sponsor

Subjects who discontinue from study treatment (for reasons other than progressive disease) should continue to be followed for progression.

Subjects who discontinue all study treatment but remain on study for disease progression assessment will have an End of Treatment (EOT) visit and will continue to be followed for adverse events (treatment-related AEs and disease-related AEs), disease progression and other protocol required procedures (see [Section 5, Table 2](#) for EOT and follow up assessment schedule). All new treatment-related AEs occurring within 30 calendar days from treatment discontinuation must be reported and followed until resolution, unless, in the opinion of the investigator, these events are not likely to improve because of the underlying disease. In this case the investigators must record the reason for not conducting the 30-day safety evaluation in the subject's medical records and as a comment on the electronic Case Report Form (eCRF).

All subjects who have CTCAE Grade 3 or 4 laboratory abnormalities at the time of withdrawal should be followed until the laboratory values have returned to Grade 1 or 2, unless in the opinion of the investigator, it is not likely that these values are to improve because of the underlying disease. In this case, the investigator must record his or her reasoning for making this decision in the subject's medical records and as a comment on the eCRF.

Subjects who discontinue from the study will have an End of Study visit (EOS - see [Section 5, Table 2](#))

No formal futility analysis of efficacy or safety will be conducted in this study, however if [Study 304](#) is closed for futility for either safety or efficacy reasons, then this Study UTX-TGR-204 will also be terminated.

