Procedures 	Off Protocol Treatment for Non-PD (AE, investigator decision, etc.) NOT Receiving Non-Protocol Treatment	Off Protocol Treatment for Non-PD (AE, investigator decision, etc.) Receiving Non-Protocol Treatment	Off Protocol Treatment for PD
ECOG Performance Status	X		
Physical Exam	X		
Vital Signs	X		
Hematology	X		
Chemistry	X		
MRD	X		
Con Meds	To be followed for 30 days after last day of study drug(s)		
AE Evaluation	To be followed for 30 days after last day of study drug(s)		
Tumor Evaluations 	X		
EOT Page	X	X	X
Post Treatment Visits	X		
EOS Visit 		X	X

 PFS off treatment should be assessed per institutional standard of care.

 CT or MRI imaging of the Neck, Chest, Abdomen, and Pelvis should be completed per institutional standard of care. There is no central radiology review for this study.

 EOS visit should be documented in the EDC once subject has PD and/or starts non-protocol therapy.

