## 9.8.2 SECONDARY EFFICACY VARIABLES

---

Progression free survival (PFS) is defined as the time from study entry to the first documentation of tumor progression or death due to any cause whichever comes first. For subjects previously on Arm A of Study UTX-TGR-304, PFS will be calculated from the date of randomization on Study UTX-TGR-304 to the first documentation of tumor progression or death due to any cause whichever comes first. This variable will be analyzed via Kaplan-Meier methodology. The median PFS will be estimated by treatment group, if appropriate (i.e., if sample sizes are sufficient) and overall.

MRD negativity rate is defined as the proportion of subjects who are MRD negative. This variable will be analyzed by the total number and percentage of subjects who are confirmed to achieve MRD negativity as per laboratory confirmation by treatment group and overall.

Duration of response is defined as the time from documentation of a response to treatment to the first documentation of tumor progression or death due to any cause whichever comes first. For subjects previously on Arm A of Study UTX-TGR-304, unless the subject's best overall response during study UTX-TGR-304 was stable disease, the duration of response will be determined from the first documented response on Study UTX-TGR-304. Duration of the response will be summarized using n (sample size), mean, standard deviation, median, minimum and maximum for the responders by treatment group and overall.

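### Table 2 and the synopsis close follow-up at the start of non-protocol therapy, but PFS and DOR run to any progression or death and no rule covers the switch

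*Combined protocol and SAP*

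**What the plan says.** Text that ends follow-up at new therapy:

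- **Section 5, Table 2.** Subjects off treatment for reasons other than progression fall into two columns, according to whether they receive other treatment. Under "Off Protocol Treatment for Non-PD (AE, investigator decision, etc.) Receiving Non-Protocol Treatment" only the end-of-treatment page and the end-of-study (EOS) visit are marked, besides 30 days of adverse-event and medication follow-up. Tumor evaluations, MRD and post-treatment visits are marked only for those not receiving other treatment. Footnote 3: "EOS visit should be documented in the EDC once subject has PD and/or starts non-protocol therapy".
- **Synopsis, Study Design.** Off-treatment scans are "reported in the EDC until progressive disease or subject begins another anti-cancer treatment".

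Text that continues follow-up:

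- **Section 4.1.** Subjects who stop treatment and "have not progressed should continue to be followed for progression per institutional standard of care and reported in eCRF". Section 6.4.4 says much the same. Neither makes an exception for new therapy.
- **Section 4.4.** "Subjects who discontinue from study treatment (for reasons other than progressive disease) should continue to be followed for progression". It then refers to Table 2 for the schedule.
- **Synopsis and Section 4.1.** "Date of progression, beginning of new treatment, and/or death should be entered in the eCRF".
- **Sections 6.4, 6.4.1 and 6.4.2.** The EOS visit is tied to withdrawn consent or documented progression; new therapy is not mentioned.

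Endpoints: Section 9.8.2 runs both PFS and DOR to the "first documentation of tumor progression or death due to any cause whichever comes first". The synopsis and Section 2.2 agree on these events. PFS is analyzed by Kaplan-Meier with no censoring rule. DOR is summarized by n, mean, SD, median, minimum and maximum.

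**The concern.** The endpoints need events that the follow-up schedule makes no arrangement to collect. A subject who stops for toxicity or by investigator decision and then starts another therapy is closed in the study, yet PFS as defined is still running. With Kaplan-Meier and no further data, that subject is in effect censored on the day of the switch. This is harmless only if the switch is unrelated to the risk of progression or death. Some subjects may be switched because they are doing badly without formally documented progression, and censoring them would flatter PFS.

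PFS and DOR are the primary objectives for former Arm A subjects in the synopsis. They are secondary for Arms B, C and D there, and secondary for everyone in Sections 2.1 and 9.8.2. Analysis rules can be written later, but events not collected after the EOS visit may not be recoverable.

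**Working it through.** **1. The texts side by side, for a subject who stops without progression and then starts other therapy**

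| Place | Followed for progression after the switch? | EOS trigger |
|---|---|---|
| Table 2 and footnote 3 | No | Progression and/or new therapy |
| Synopsis, scan rule | No | Not stated |
| Synopsis, closing sentence | Yes, no exception | Not stated |
| Sections 4.1, 6.4.4 | Yes, no exception | Not stated |
| Section 4.4 | Yes, but schedule referred to Table 2 | Leaving the study, per Table 2 |
| Section 6.4 | Yes (stopped for toxicity), as Table 2 describes | Consent withdrawal or progression |
| Sections 6.4.1, 6.4.2 | Not stated | Consent withdrawal or progression |
| Section 8 | Yes, in line with the protocol generally | Not stated |
| PFS/DOR definitions | Events count whenever they occur | Not applicable |

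Sections 4.1 and 6.4.4 conflict plainly with Table 2, and the synopsis conflicts with itself. Sections 4.4, 6.4 and 8 conflict only in part. The column reading of Table 2 relies on extracted table text, but footnote 3 states the EOS trigger in prose.

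**2. Is there a figure to reproduce?** No. The documents give no switch rate, expected PFS, event count or power. Everything below is assumed and serves only to show range and sign.

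**3. Illustration A: some subjects are prone to switch and also have a higher hazard.** Assumed: median PFS 18 months in ordinary subjects, so h = ln 2 / 18 = 0.0385 per month; fraction p switch-prone, with hazard r·h; switch rate s = 1/8 per month in prone subjects; the switch itself does not change the hazard.

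- Full follow-up: S(t) = (1−p)·exp(−ht) + p·exp(−rht); the median solves S(t) = 0.5.
- Censored at the switch: λ(t) = [(1−p)·h·exp(−ht) + p·r·h·exp(−(rh+s)t)] / [(1−p)·exp(−ht) + p·exp(−(rh+s)t)]; the Kaplan-Meier median solves ∫λ = ln 2.
- Share switching before an event: p·s/(s + rh).

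| p | r | Share switching | Full median | Censored median | Difference |
|---|---|---|---|---|---|
| 0.1 | 2 | 6.2% | 16.74 | 17.40 | +0.66 |
| 0.1 | 3 | 5.2% | 16.09 | 16.99 | +0.91 |
| 0.2 | 2 | 12.4% | 15.55 | 16.73 | +1.19 |
| 0.2 | 3 | 10.4% | 14.28 | 15.89 | +1.61 |
| 0.3 | 2 | 18.6% | 14.44 | 16.01 | +1.56 |
| 0.3 | 3 | 15.6% | 12.64 | 14.68 | +2.05 |
| any | 1 | 7.6–22.9% | 18.00 | 18.00 | 0 |

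Check for p = 0.2, r = 3 at 14.28 months: 0.8·exp(−0.550) + 0.2·exp(−1.650) = 0.462 + 0.038 = 0.500.

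**4. Illustration B: the hazard changes at the switch.** Assumed: h = ln 2 / 24 = 0.0289 per month before the switch; share q switches first, so the switch hazard is g = h·q/(1−q); hazard m·h afterwards. Switching is unrelated to the pre-switch hazard, so the censored median stays at 24.0 months. With full follow-up, S(t) = exp(−(h+g)t) + g·[exp(−mht) − exp(−(h+g)t)] / (h + g − mh).

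| q | m = 0.5 | m = 1 | m = 2 | m = 3 |
|---|---|---|---|---|
| 0.1 | 24.5 | 24.0 | 23.3 | 22.9 |
| 0.2 | 25.2 | 24.0 | 22.6 | 21.7 |
| 0.3 | 26.1 | 24.0 | 21.7 | 20.5 |

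Against PFS as 9.8.2 defines it, the censored median runs from 24.0 − 20.5 = 3.5 months too long to 26.1 − 24.0 = 2.1 months too short. The sign depends on m, about which the documents say nothing.

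**5. DOR.** Kaplan-Meier is not specified here. A mean and SD need a number for every responder. For one who switches without an event the plan supplies none: time to the switch would understate duration, and leaving the subject out changes the group being described.

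**The case against.** The strongest reply is that stopping at new therapy is deliberate and largely consistent. Table 2's columns, footnote 3 and the synopsis scan rule agree. Section 4.4 and Section 6.4 send the reader to Table 2, and Section 8 defers to the protocol. On that reading only Sections 4.1 and 6.4.4 and one general sentence in the synopsis lack the pointer. The study is descriptive, without hypothesis tests or powering. Following subjects through a switch also credits or blames the study combination for the next therapy.

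Much of this stands. Censoring at new therapy is a legitimate choice, and which analysis should lead is a trade-off. But the choice must appear in 9.8.2, and it does not. The EOS triggers in 6.4, 6.4.1 and 6.4.2 also differ from footnote 3, and a reported median can mislead without a test attached.

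Stronger readings that a reader might infer but the documents do not support:

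- *Later events are never recorded.* The synopsis and 4.1 ask for those dates; what is missing is any contact after the EOS visit.
- *PFS and DOR are both biased upward.* For PFS the sign is assumed: Table 2's examples of non-progression reasons are adverse events and investigator decision, not poor disease control. For DOR the Kaplan-Meier argument does not apply.
- *Responses to the next therapy inflate ORR.* Section 8.3 does let best response run until progression, but Table 2 and the synopsis schedule no tumor evaluation after the switch. The risk arises only if follow-up is extended without a cut-off.

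**Conclusion.** The concern holds as an unreconciled conflict and a missing rule. The schedule closes switchers, 4.1 and 6.4.4 keep following them, and the endpoint definitions need the events. PFS as defined therefore cannot be measured reliably in subjects who switch before progression, and DOR is undefined for responders who do so.

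Size is illustrative only: roughly 0.7 to 2.1 months too long on an 18-month median if 10–30% are switch-prone with 2–3 times the hazard, nil if hazards are equal, and the opposite sign if the next therapy lowers the hazard. It is not established that the plan overstates PFS, nor that PFS and DOR are primary for the whole study. Importance is moderate: the study is descriptive, and the endpoints are primary only for Arm A and only in the synopsis. Correction is still worthwhile because it costs little and the data may not be retrievable later.

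**What to change.** 1. Align Table 2, footnote 3 and the synopsis with Section 4.1. For subjects who stop without progression and start other therapy, record the start date of the new therapy, the first progression date (from routine care, no protocol scans) and the date of death, until progression, death, consent withdrawal or study closure. Do not document EOS merely because new therapy has started.
2. State in 9.8.2 how new therapy is handled for PFS and DOR: either events count as now defined, with censoring at new therapy as a sensitivity analysis, or the reverse. For DOR, say how a responder without an event is summarized.
3. Count best response and MRD only from assessments made before new therapy.

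The cost is small: wording changes, date fields the protocol already requests, and light date-only follow-up of those who switch without progression. The downsides are a possibly less favorable PFS and post-switch events that partly reflect the next therapy, which is why both analyses should be reported. Collecting the dates keeps either analysis possible.

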## 5.1 LABORATORY EVALUATIONS - OVERVIEW

All subjects should visit the study center on the days specified within this protocol. The complete schedule of assessments is shown in [Section 5](#). The baseline physical examination with vital signs, medical history, Rai staging, evaluation of concomitant medications, ECOG PS, bone marrow aspirate/biopsy (if applicable), complete blood count/full blood count (3-part differential accepted), serum chemistry, and CLL FISH panel, should be done within 28 days prior to initiation of treatment (14 days for CBC and Chemistry). For women of child bearing potential, a serum pregnancy test should be completed within 3 days (72 hours) prior to Day 1 of Cycle 1 and a urine pregnancy test within 3 days of assessment as per the [table in Section 5](#). Tumor assessment scans should be performed  $\leq 45$  days prior to initiation of treatment. In the event that the subject's condition is deteriorating, laboratory evaluations should be repeated within 48 hours prior to initiation of the next cycle of therapy.

### 5.1.1 LABORATORY EVALUATIONS (LOCAL LAB)

1. Hematologic profile and serum chemistry to include:

Serum Chemistry		
Albumin	Creatinine	SGOT [AST]
Alkaline phosphatase	Glucose	SGPT [ALT]
Bicarbonate/ CO 2	LDH	Sodium
BUN	Magnesium	Total bilirubin
Calcium	Phosphorus	Total Protein
Chloride	Potassium	Uric acid
Hematologic Profile		
Hematocrit	Neutrophils	Platelet count
Hemoglobin	Lymphocytes	
Erythrocyte count	Monocytes	
Absolute neutrophil count	Eosinophils	
Absolute leukocyte count	Basophils	

2. Serum and urine pregnancy tests
3. Baseline bone marrow aspirate/biopsy (if applicable)
4. CLL FISH Panel
5. MRD for subjects in CR or PR beginning at Cycle 6 response assessment
6. Serum Virology to include HBsAG, HBc antibody, HCV antibody, and CMV IgG and IgM. If HBc antibody, HCV antibody or CMV IgM are positive the subject must be evaluated for the presence of active HBV, HCV or CMV by PCR - See [Appendix D](#). For all subjects approximately every 3 months CMV screening by PCR. CMV surveillance will discontinue 30 days after last dose of umbralisib, or as otherwise clinically indicated per investigator discretion.

## 6 TREATMENT PLAN

---

### 6.1 TREATMENT SUMMARY

---

Treatment will be administered on an outpatient basis in 4-week (28 day) cycles for subjects that roll over from 304 Arms B, C, and D.

#### Treatment Schema for Subjects Crossing over from Arm A:

Subjects who crossover from Treatment Arm A will continue their treatment where they left off at the termination of [protocol UTX-TGR-304](#).

#### Treatment Schema for Subjects Crossing over from Arms B and D:

##### Cycle 1:

Ublituximab			TGR-1202
Day 1	Day 2	Day 8 & 15	Daily
150 mg	750 mg	900 mg	800 mg

##### Cycles 2 through 6:

Ublituximab	TGR-1202
Day 1	Daily
900 mg	800 mg

##### After Cycle 6:

Ublituximab	TGR-1202
Day 1, Q3 months	Daily
900 mg	800 mg

#### Treatment Schema for Subjects Crossing over from Arm C:

Cycle 1 should start 28 days after the last dose of ublituximab (given on the 304 study)

##### Cycles 1 through 6:

Ublituximab	TGR-1202
Day 1	Daily
900 mg	800 mg

##### After Cycle 6:

Ublituximab	TGR-1202
Day 1, Q3 months	Daily
900 mg	800 mg

### 6.2 AGENT ADMINISTRATION

---

Ublituximab treatment will be administered as an IV infusion while TGR-1202 will be administered orally, both on an outpatient basis.

---

## 6.2.1 GUIDELINES FOR ADMINISTRATION OF UBLITUXIMAB

---

- *Method of Administration:* Ublituximab will be administered as an intravenous infusion through a dedicated line.
- *Potential Drug Interactions:* No Drug Interactions have been reported to date.
- *Pre-medications:* Ublituximab should be started approximately 30 minutes after the conclusion of the last pre-medication infusion and should include an antihistamine (diphenhydramine 50 mg or equivalent), and a corticosteroid (dexamethasone 10-20 mg or equivalent). If pre-medication is given orally, they should be given approximately 45-60 minutes prior to the beginning of the ublituximab infusion. After C1 adjustments can be made to the antihistamine and/or corticosteroid dosing should subject exhibit adverse effects from the agents or have a medical condition the pre-medications adversely impacts after discussion with TG Therapeutics contact.
  - Use of oral acetaminophen 650 mg (or equivalent) should be restricted to subjects who experience fever or pyrexia after week 1 dose, or as clinically warranted.
- *Hypersensitivity and Infusion Reaction Precautions:* Medication and resuscitation equipment must be available per institutional guidelines prior to ublituximab administration for the emergency management of potential anaphylactic reactions.
- *Subject Care Implications:*
  - Ublituximab should not be administered as an IV push or bolus.
  - Diluted ublituximab should be checked before administration for cloudiness, color, or deposits. Ublituximab should not be administered if does not conform to the specifications. Immediately inform the Monitor/Sponsor with any product quality concerns or questions.
  - It is recommended that ublituximab be administered immediately after dilution.
  - No other treatment may be co-administered with ublituximab (other than for immediate intervention for adverse event).
  - Concurrent glucocorticoid therapy as long as started for at least 7 days prior to study entry ( $\leq 10$  mg per day of prednisone or equivalent) is allowed as clinically warranted.
  - Since infusion-related hypotension may occur, consider holding antihypertensive medications 12-24 hours prior to and throughout infusion of ublituximab.
  - For subjects at risk for tumor lysis syndrome in the opinion of the treating investigator, prophylaxis with allopurinol or per recommended institutional standards should be considered.

---

### 6.2.1.1 INFUSION RELATED REACTIONS AND INFUSION RATE GUIDANCE - UBLITUXIMAB

---

Infusion related reactions including severe reactions have been reported with ublituximab administration in subjects with CLL. Guidelines are provided below for subjects who experience such reactions. Symptomatic infusion reactions, despite premedication, may be treated at the discretion of the treating physician, including but not limited to: oral acetaminophen 650 mg (or equivalent), corticosteroids, antihistamines, oxygen, and bronchodilators.

The following are recommended infusion rate reduction/delay guidelines for subjects who experience severe Infusion Related Reactions (IRR's) in which treatment should be interrupted. Final decision for infusion rate reduction/delay or discontinuation resides with the treating investigator.

